6.0 ADVERSE EVENTS

6.1. Adverse Event Definitions

6.1.1 Adverse Events (AE) is any unfavorable and unintended sign (including an abnormal laboratory finding), symptom or disease temporally associated with the use of a medicinal (investigational) product, treatment or procedure regardless of whether it is considered related to the medical treatment or procedure (*NCI CTEP Guidelines March 28, 2011*).

6.1.2 Serious Adverse Event (SAE) is an AE that is fatal or life threatening, requires inpatient hospitalization or prolongation of existing hospitalization (for > 24 hours), persistent or significant incapacity or substantial disruption of the ability to conduct normal life functions, or is a congenital anomaly/ birth defect, or results in any important medical event that may not result in death, be life threatening, or require hospitalization may be considered an SAE when, based upon appropriate medical judgment, may jeopardize the subject and may require medical or surgical intervention to prevent any of the above outcomes. A "life-threatening" adverse event places the patient at immediate risk of death in the judgment of the investigator or sponsor.

6.1.3 Severity Rating

The investigator will evaluate the severity of each adverse event. NCI Common Terminology Criteria for Adverse Events (CTCAE v.4.0) or study specific toxicity tables provided in the protocol define severity. If not included in CTCAE v.4.0, severity is expressed in numerical grade using the following definitions:

- 1. Grade 1: Mild-asymptomatic or mild symptoms; clinical or diagnostic observations only; intervention not indicated.
- 2. Grade 2: Moderate-minimal, local or noninvasive intervention indicated; limiting age appropriate instrumental ADL.
- 3. Grade 3: Severe-severe or medically significant but not immediately life-threatening; hospitalization or prolongation of hospitalization indicated; disabling; limiting self care ADL.
- 4. Grade 4: Life-threatening consequences; urgent intervention indicated.
- 5. Grade 5: Death related to AE

6.1.4 Attribution/Relationship to study drug

- 1. Definite clearly related
- 2. Probable likely related
- 3. Possible may be related
- 4. Unlikely doubtfully related
- 5. Unrelated clearly not related

6.1.5 Expectedness

An Expected Adverse Event is one where the specificity or severity is consistent with the current information available from the resources.

An Unexpected Adverse Event is one where the nature, severity, or frequency of the event is related to participation in the research is not consistent with either:

- 1. The known or foreseeable risk of adverse events associated with the procedures involved in the research that are described in (a) the protocol-related documents, such as the IRB-approved research protocol, any applicable investigator brochure, and the current IRB-approved informed consent document, and (b) other relevant sources of information, such as product labeling and package inserts: or
- 2. The expected natural progression of any underlying disease, disorder, or condition of the subject (s) experiencing the adverse event and the subjects(s) predisposing risk factor profile for the adverse event.

6.2 Recording and Reporting Responsibilities

6.2.1 Investigative Site Recording Responsibilities:

- 1. Upon identification of an AE or SAE, the site investigator will utilize the above definitions to properly classify the event. Each category listed above must be recorded for each event.
- 2. All AEs and SAEs will be recorded in the "AE case report forms" (CRF) and in progress reports with details about the grade and attribution of each episode, action taken with respect to the study drug, and the patient's outcome will be recorded in the CRF. All events will be recorded on case report forms for the duration of the study until they resolve.
- 3. All SAEs will be recorded on the FDA MedWatch form 3500a. After submitting the initial report it may be necessary to submit follow up reports to the OCR, Sponsor and the FDA should the event require further investigation.

6.2.2 Investigative Site Reporting Responsibilities:

1. The investigator/ site is responsible to report all SAEs that occur on or after the first day of study treatment to the sponsor within 24 hours of becoming aware of the event. All subsequent SAEs must be reported for up to 30 days after the last

treatment.

Each investigator is responsible to report all AEs/SAEs to their local IRB following guidelines set by that IRB. The FCCC OCR reserves the right to request an event be reported to the IRB at their discretion. Copies of events reviewed by the IRB must be sent email to **[contact]**.

- 2. If the investigator or IRB feels the event warrants a revision to the informed consent that was not already initiated by the OCR, draft revisions will be made in track changes and submitted to the OCR for consideration. Any consent revisions must receive OCR approval **prior** to submission to the IRB.
- 3. Any investigator who is in doubt of whether a particular AE needs to be reported is directed to call the Study Monitor for confirmation with the Sponsor Investigator
- 4. If the results of an investigator or OCR investigation show an adverse event not initially determined to be reportable is so reportable, the investigator will report the event following the above guidelines based on the date the determination is made.
- 5. Copies of all related correspondence and reporting documents must be submitted to the ISRU and will be maintained in the trial master file.

Participating sites should report events to:

Investigator-Sponsored Research Unit Office of Clinical Research Fox Chase Cancer Center [contact]

6.2.3 Sponsor Reporting Responsibilities:

- 1. Adverse events which meet all of the following criteria must be reported to all participating institutions for IRB submission within 2 weeks of notification of the event.
 - i. Unexpected (in terms of nature, severity, or frequency) given (a) the research procedures that are described in the protocol-related documents, such as the IRB-approved research protocol and informed consent document; and (b) the characteristics of the subject population being studied;
 - ii. Possibly related to participation in the research (possibly related means there is a reasonable possibility that the incident, experience, or outcome may have been caused by the procedures involved in the research); and
 - iii. Serious (refer to above definition) or otherwise one that suggests that the research places subjects or others at a greater risk of physical or psychological harm than was previously known or recognized.
- 2. If the adverse event requires modification of the study protocol and informed consent, these changes will be provided to all participating institutions in the form of an amendment from the OCR for each site's IRB of record along with the report of the adverse event.

- 3. Copies of all related correspondence and reporting documents will be maintained in a centralized regulatory file for this study at OCR.
- 4. SAEs that are related, unexpected, fatal, or life threatening are reportable through the Food and Drug Administration (FDA) MedWatch program by telephone or fax no later than 7 calendar days after initial receipt of the information. Further information on the timing of submissions are as directed by FDA guidelines (http://www.fda.gov/medwatch/index.html). Serious, unexpected events that suggest significant clinical risk will be submitted to within 15 calendar days after initial receipt of this information.

Food and Drug Administration: [contact] [contact] http://www.fda.gov/medwatch/report.htm

6.3 Pregnancy

All WOCBP should be instructed to contact the Investigator immediately if they suspect they might be pregnant (e.g., missed or late menstrual period) at any time during study participation.

In the event of a confirmed pregnancy in a patient participating in the study, the Investigator must immediately notify the Study Monitor at [contact] who will notify [name].

7.0 CONCOMITANT MEDICATIONS, CAPECITABINE AND QUINACRINE

The concomitant use of quinacrine and primaquine is contraindicated. Since quinacrine concentrates in the liver, it should be used with caution in conjunction with hepatotoxic drugs and in patients with hepatic disease or alcohol dependence. Alcohol or alcohol-containing medications is not recommended during quinacrine treatment (quinacrine has been reported to produce a mild Disulfram-like reaction when ingested with alcohol, which may be due to quinacrine's inhibition of the intermediary metabolism of alcohol; ingestion of alcohol or alcohol containing medications is not recommended during quinacrine treatment). Patients receiving any medications or substances that are substrates of CYP2C9 enzyme are ineligible because Capecitabine inhibits CYP2C9.

7.1 Investigational Agents

Delivery of medications: Study drug – Quinacrine will be ordered and delivered to the investigational drug pharmacy, and then given to the patient on day 1 of each cycle. Capecitabine is available commercially.

	Quinacrine (NSC#: 14229)	Capecitabine (NSC#:71280)
Available dosage forms	100 mg capsules	150 mg and 500 mg tablets

Route of administration	Oral administration with a glass of water within 30 minutes after a meal	Oral administration within 30 minutes after a meal
Supplier	Philadelphia Professional Compounding Pharmacy	Commercial Supply

7.2 Capecitabine

NSC#: 712807

Supplier: Commercially Available

Hematologic

Hematologic side effects including lymphopenia (58% to 94%), anemia (44% to 74%), neutropenia (16% to 22%), and thrombocytopenia (15% to 21%) have been reported. Cases of severe hypertriglyceridemia induced by capecitabine have also been reported.

Gastrointestinal

Gastrointestinal side effects including diarrhea (50%), nausea (44%), vomiting (26%), stomatitis (23%), abdominal pain (17%), constipation (9%), and dyspepsia (6%) have been reported. A case of capecitabine-induced pancreatitis has also been reported.

Dermatologic

Dermatologic side effects including hand and foot syndrome (35% to 45%), dermatitis (23% to 31%), nail disorder (4%), alopecia, erythematous rash, pruritus, eruptive multiple lentigo maligna-like lesions, radiation recall dermatitis, pyogenic granulomas, photoeruption, hyperpigmentation, inflammatory responses in actinic keratosis have been reported. A case of leopard-like vitiligo and a case of subacute cutaneous lupus erythematosus have also been reported.

Hepatic

Hepatic side effects including hyperbilirubinemia (34%) and hepatic failure have been reported.

General

General side effects including fatigue (34%), pyrexia (10%), and limb pain (4%) have been reported.

Metabolic

Metabolic side effects including anorexia (20%) and dehydration (5%) have been reported.

Nervous system

Nervous system side effects including paresthesia (12%), headache (7%), dizziness (5%), and insomnia (3%) have been reported. A case of cerebellar ataxia has also been reported.

Ocular

Ocular side effects including eye irritation (10%) and lacrimal duct stenosis have been reported.

Cardiovascular

Cardiovascular side effects including edema (6%) have been reported. Three cases of severe

angina-like chest pain possibly or probably related to Capecitabine treatment have been reported. One case of Capecitabine-induced coronary vasospasm has also been reported.

Musculoskeletal

Musculoskeletal side effects including myalgia (4%) have been reported.

Other

Other side effects including a case of tumor lysis syndrome have been reported.

Over dosage of capecitabine would be expected to cause nausea, vomiting, diarrhea, GI irritation and bleeding, and bone marrow depression. Patients receiving capecitabine 1657 mg/sq m daily (as 2 divided doses) in a continuous daily regimen for at least 6 weeks experienced severe palmar-plantar erythrodysesthesia, mucositis, and diarrhea [25].

Patients experiencing any of the following adverse effects of capecitabine at the severity described should immediately discontinue capecitabine therapy and promptly notify their clinician nocturnal stools or an increase of 4-6 stools daily or greater, nausea with a substantial decrease in food intake, frequent vomiting (i.e., 2-5 or more episodes of vomiting in a 24-hour period), painful erythema and swelling of the hands and/or feet that results in discomfort, affecting activities of daily living, painful erythema, edema, or ulcers of the mouth or tongue. Patients who develop a fever of 100.5 degree Fahrenheit or greater or other evidence of potential infection should promptly notify their clinician [25]. Capecitabine should be avoided in elderly patients with renal dysfunction or overlapping toxicities.

7.3 *Quinacrine* NSC #[.] 14229

Supplier: Philadelphia Professional Compounding Pharmacy [name]

Adverse reactions were shown to be mostly minor. Many of quinacrine's side effects develop gradually and have been found to be completely and easily reversible, if quinacrine use is discontinued at this early stage [28, 65-68].

Hematologic

Aplastic anemia - increased reports from 0.66/100,000 to 2.84 with using of quinacrine during World War II – in this report, 48 out of 57 patients were receiving quinacrine.

Gastrointestinal

Gastrointestinal side effects including abdominal cramping, diarrhea, reversible hepatitis reported in high dose (300mg daily), one case report of peritonitis on high dose. Mild anorexia, nausea has also been reported.

Dermatologic

Dermatologic side effects including rashes (1.67%) – eczematous rash is most common, rest can be lichenoid, and exfoliative. Lichen planus reported in 1/2000 soldiers who received 100mg daily, and 1/500 in ones received 200mg daily.

Quinacrine temporarily imparts a yellow color to the urine and skin; however the drug does not cause jaundice [55]. Patients should be counseled regarding urine discoloration and/or skin discoloration. Since quinacrine may precipitate severe attacks of psoriasis and may exacerbate porphyria, the drug should not be used in patients with these conditions unless the potential benefits justify the possible risks [55].

Hepatic

Long-term high dose use was occasionally associated with reversible hepatitis.

General

General side effects include mild transient headache, dizziness (33%).

Metabolic

Metabolic side effects including anorexia (20%) and dehydration (5%) have been reported.

Nervous system

Nervous system side effects including fast frequencies in EEG have been reported. High dose usage can rarely be associated with restlessness, vertigo, insomnia, nightmares, hyperirritability, psychosis and convulsion (0.1-0.4% reported).

Ocular

Only one retinotoxicity case has been reported. High dose use can be associated with hypersensitivity reaction as corneal edema, reported in 600mg daily dose.

Cardiovascular

No known cardiovascular side effects. Musculoskeletal No known musculoskeletal side effects.

Other

Quinacrine is an oxidizing agent and can cause methemoglobinemia or hemolytic anemia especially in patients with glucose-6-phosphate dehydrogenase (G6PD) deficiency [69]. It should be administered with caution to patients with glucose-6-phosphate dehydrogenase deficiency [55].

Toxicity: Although some adults have survived single quinacrine hydrochloride doses up to 25 g, a dose of 6.8 g has been fatal when given intraduodenally. Symptoms of acute quinacrine toxicity include CNS excitation with restlessness, insomnia, psychic stimulation, and seizures; GI disorders; vascular collapse with hypotension, shock, cardiac arrhythmias or arrest; and yellow skin pigmentation [55].

8. CORRELATIVE/SPECIAL STUDIES

8.1 Laboratory Correlative Studies

8.1.1 Pharmacokinetic (PK) study

Pharmacokinetic information including Cmax, T1/2(half-life) and AUC of investigational drugs capecitabine and quinacrine will be collected as exploratory objectives of phase I and II parts of the study. Given linear kinetics of quinacrine, and a short half-life (4hrs) from previous human study data, blood sample for pharmacokinetic (PK) analysis in this study will be collected on 5 different time points on day 1 of cycle 1, and on day 1 of cycle 2 and cycle 3. For pharmacokinetic analysis, 4.5mL of blood will be drawn into a lithium heparin tube at each time point.

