Pharmacokinetics: Quinacrine is usually administered orally with a full glass of water after a meal [26, 32, 33, 35, 43-45]. It is absorbed quickly after oral administration with plasma levels increasing 2-4 hours after administration and reaching a peak in 8-12 hours [26, 46, 47]. Plasma concentration increases fast during the first week and equilibrates by the fourth week [48, 49]. The highest concentrations of quinacrine are found in the liver, spleen, lungs, and adrenal glands, lowest are found in the brain, heart, and skeletal muscle [47]. Concentration in the liver may be 20,000 times that in the plasma [50]. Quinacrine is deposited in the skin, fingernails and hair [26]. The drug crosses the placental barrier and, concentrations in fetal tissue are similar to maternal concentrations [51, 52]. Cerebrospinal fluid concentrations are 1 to 5% of corresponding plasma level [47]. 80-90% of the drug is bound to plasma proteins when given at therapeutic doses. Half-life of the drug is 5-14 days depending on the dosing regimen [48, 53]. Excretion of quinacrine occurs principally through the urine where less than 11% is eliminated daily. Small amounts are excreted in bile, sweat, saliva and breast milk [47]. Elimination via the renal system may be enhanced by acidification and reduced by alkalization [26, 46, 47]. Quinacrine may be detected in the urine up to 2 months after therapy has been discontinued.

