3.0 STUDY DESIGN

3.1 Phase I

Because of the well published safety profiles of both quinacrine and capecitabine, the Phase I portion of our study will aim to determine the tolerability of both agents in combinations when used at established clinical doses. Given that capecitabine is considered as standard treatment for mCRC, a full dose of 1000mg/m² orally bid of capecitabine will be administered with different doses of quinacrine. The maximum dose of quinacrine to be tested is 200 mg bid. The first patient in this study will be treated with 1000 mg/m² orally bid of capecitabine on days 1-14, and a starting dose of 100 mg orally daily of quinacrine on days 1-21 of a 21 day cycle (dose level -2 in table below). All patients will be evaluated for baseline toxicity. Toxicity will be evaluated according to the National Cancer Institute Common Toxicity Criteria (current version 4.0).

A modified version 4B of Simon's accelerated titration design (Figure 3) will be used in the Phase I portion of our study to limit the number of patients treated at potentially sub therapeutic doses [60]. In this design, a cohort has at least one patient treated at a dose level (designated as "i"). If no DLT is observed (i.e. no toxicity, T, >2) at cycle 1, another single-patient cohort is treated with the next higher dose level (i.e., "Add 1 to i"). On the other hand, if a DLT is observed in a single- patient cohort in the first cycle, an additional two patients are treated at the same dose level (i.e. Dose i 2 patients). If another instance of toxicity > grade 2 is observed, three additional patients will be treated at that dose level. If at most 2 of the 6 patients treated at a dose level experience a DLT, that dose level is identified as the MTD.

Dose Escalation		
	Dose *	
Dose Level	Quinacrine (mg)	Capecitabine (mg/m2)
Level -2	100, qd	1000 bid

Level -1	100, bid	1000 bid
Level 0	200, bid	1000 bid

Adopting the modified version 4B of Simon's accelerated titration design, it is possible that only three patients are enrolled in Phase I. This situation can occur in the event that the first patient that received dose level -2, the first patient that received dose level -1 and the first patient that received dose level 0 do not experience toxicity>2.

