*NA indicates that the action taken is the same regardless of whether there were patients previously treated at a higher dose

The MTD will be used at recommended phase 2 dose (RP2D) unless there are any safety concerns. Patients who needed a dose reduction after being treated with RP2D in phase I will receive the reduced dose in phase II.

For the purposes of quinacrine dose escalation, the dose-limiting toxicities (DLT) that will be taken into account include toxicity grade >2 hematological, GI/diarrhea, skin, LFT abnormality or otherwise unexpected grade 3 toxicity or higher, associated with the combination therapy. Quinacrine dose modifications will not be made in the event of toxicities that are primarily attributed to capecitabine; namely, > grade 2 alopecia and hand and foot syndrome (HFS). Patients experiencing DLT will be permitted to continue their treatment after a single step dose reduction.

Intra-patient dose escalation will occur only for patients experiencing Common Toxicity Criteria < grade 2 toxicity on a previous course. The intra-patient dose escalation for a patient in lower level dose cohort will be on hold until the highest dose cohort patient completes first cycle of therapy. For purposes of toxicity assessment, patient response to the initial dose received will be considered. Total time in therapy, however, will be adjudged to include the whole duration the patient received treatment, regardless of the doses received.

General concomitant medications, dose adjustment, drug warnings and supportive care guidelines, duration of therapy, duration of follow up, and criteria for removal from treatment, as described throughout the protocol will be applied to both Phase I and II.

The endpoint of the Phase I portion of this study will occur when the safety and tolerability of the quinacrine-capecitabine combination is evaluated. Based on our preclinical data and the history of use of both capecitabine and quinacrine, we expect that the following regimen will be safely tolerated by the majority of patients.

	Premedications;				Cycle
Agent	Precautions	Dose	Route	Schedule	Length
Quinacrine	After a meal with a	200 mg tablets	Orally:	Daily on	
	glass of water	Orally twice a	at least 8 hours	Days 1-21	
		day	between each		
			dose		
Capecitabine*	Within 30 minutes	1000 mg/m ²	Orally:	Daily on	21 days
	after a meal with	Orally twice a	at least 8 hours	Days 1-14	(3 weeks)
	water	day	between each		
			dose		

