*The calculated total daily capecitabine dose by body surface area (BSA) will be rounded down to allow doses using 500mg tablets

After finishing cycle #1, start cycle #2 on day 22, and continue every 21 days.

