5.0 Treatment Modifications

5.1 Dose Reductions

In the event of alopecia, HFS, or stomatis, only capecitabine dose will be reduced according to the following table.

Hand and Foot	Management/Next Dose for Capecitabine		
Syndrome/Stomatitis/Alopecia			
Grade 1	No change in dose		
Grade 2	Hold until \leq Grade 1. Resume at same dose level.		
Grade 3	Hold until < Grade 1. Resume at one dose level lower, if		
Glade 5	indicated. (Per Section 5.2 Dose Levels)		
Grade 4	Off protocol therapy		

In the event of other toxicities that are specifically attributable to capecitabine (such as hand-foot syndrome, diarrhea), the dose of capecitabine will be delayed or reduced first. If toxicity progresses or does not improve within 72 hours after capecitabine delay or reduction, quinacrine will also be delayed/ dose-reduced. Dosing delays/modifications will be done according to the following schema:

Diarrhoa	Management/Next Dose for	Management/Next Dose for	
Diamiea	quinacrine	capecitabine	
Grade 1	No change in dose	No change in dose	
	Hold until \leq Grade 1. Resume at	Hold until \leq Grade 1. Resume at	
	same dose level.	same dose level. If it reoccurs, hold	
Grade 2		until < Grade 1 and resume at one	
		dose level lower. (Per Section 5.2	
		Dose Levels)	
	Hold until < Grade 1. Resume at	Hold* until < Grade 1. Resume at	
Grade 3	one dose level lower, if indicated.	one dose level lower, if	
Clauc 5		indicated.** (Per Section 5.2 Dose	
		Levels)	
Grade 4	Off protocol therapy	Off protocol therapy	
Recommended management: Loperamide antidiarrheal therapy			
Adjunct anti-diarrheal therapy is permitted and should be recorded when used.			

All other toxicities	Management/Next Dose for	Management/Next Dose for	
All other toxicities	quinacrine	capecitabine	
Grade 1	No change in dose	No change in dose	
Crada 2	Hold until \leq Grade 1. Resume at	Hold until \leq Grade 1. Resume at	
Grade 2	same dose level.	same dose level.	
	Hold until < Grade 1. Resume at	Hold until < Grade 1. Resume at	
Grade 3	one dose level lower, if indicated.	one dose level lower, if indicated.	
		(Per Section 5.2 Dose Levels)	
Grade 4	Off protocol therapy	Off protocol therapy	

Recommended management for nausea: antiemetics

If treatment needs to be held for more than 3 weeks due to severe treatment related toxicities that cannot be resolved despite maximum supportive care, the patient will be taken off protocol therapy.

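### Quinacrine PK sampling rests on a 4 h half-life that section 1.4 contradicts (5-14 days); on the section 1.4 figures the draws give no slope for the planned T1/2, and AUC has no stated interval

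*Combined protocol and SAP*

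**What the plan says.** Section 8.1.1 lists Cmax, T1/2 and AUC of both drugs as exploratory PK outputs and bases the schedule on "Given linear kinetics of quinacrine, and a short half-life (4hrs) from previous human study data". It cites no source for the 4 h. Section 11.5 repeats Cmax, T1/2 and AUC for quinacrine, to be shown graphically and summarised. Neither section gives an AUC interval or a method for estimating T1/2.

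Section 1.4, with citations, describes a much slower drug:
- "Half-life of the drug is 5-14 days depending on the dosing regimen"
- "plasma levels increasing 2-4 hours after administration and reaching a peak in 8-12 hours"
- "Plasma concentration increases fast during the first week and equilibrates by the fourth week"

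It also puts daily urinary elimination below 11%.

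The sample tables in section 8.1.3 and Appendix A place PK draws at 0, 1, 2, 4 and 8 h on cycle 1 day 1 (C1D1), with one pre-dose draw on C2D1 and one on C3D1. The study calendar shows PK in cycles 1 to 3 only, and section 8.2 rules out samples after the final cycle. The end-of-treatment blood is marked in the calendar's banking row, not its PK row.

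Quinacrine is taken without a planned break. The starting regimen is "100 mg orally daily of quinacrine on days 1-21 of a 21 day cycle", and section 3.1 adds "After finishing cycle #1, start cycle #2 on day 22, and continue every 21 days".

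**The concern.** A sampling schedule has to match the time scale of the drug. An 8 h window suits a 4 h half-life but not one of 5-14 days, and least of all when the peak comes at 8-12 h. Sections 1.4 and 8.1.1 cannot both describe the same half-life, and the documents do not say, for example, that 4 h refers to an early distribution phase.

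Two planned outputs are at stake. A quinacrine half-life read from a slope would have no post-peak data behind it. An AUC without an interval could mean quantities that differ many-fold.

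**Working it through.** **The stated figure.** The 4 h value is given without inputs or source, so it cannot be re-derived. It can only be set against section 1.4.

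**1. Size of the conflict.** 5 days = 120 h and 14 days = 336 h.
- Ratio: 120/4 = 30; 336/4 = 84.
- Half-lives covered by 8 h of sampling: 8/4 = 2; 8/120 = 0.067; 8/336 = 0.024.

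**2. Which scale fits the rest of section 1.4.** First-order elimination, half-life T.
- Daily loss, 1 - 2^(-24/T): 98.4% at 4 h, 12.9% at 5 d, 4.8% at 14 d. If the section's 11% limit is read as total elimination, it corresponds to ln 2 / -ln(0.89) = 5.9 d.
- Share of steady state at 28 d, 1 - 2^(-28/T), T in days: 97.9% at 5 d, 75.0% at 14 d. A 4 h half-life reaches 95% in 4 x ln 20 / ln 2 = 17.3 h.

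These statements do not all fit both ends of 5-14 days, but they point to days, not hours.

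**3. Is there a slope on C1D1?** Take the case most favourable to seeing one, instant absorption. The fall from 4 h to 8 h is 1 - 2^(-4/T):
- 4 h: 50%
- 5 d: 2.3%
- 14 d: 0.8%

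Absorption is not instant in section 1.4. With a peak at 8-12 h, the last C1D1 draw is at the peak or before it. That follows from the timing alone and holds whichever half-life is right.

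**4. Illustration with absorption.** Assume one compartment and first-order absorption, with C(t) proportional to exp(-ke(t - lag)) - exp(-ka(t - lag)), ke = ln 2/T, and ka solved from tmax - lag = ln(ka/ke)/(ka - ke). The inputs are tmax 8 or 12 h and T 5 or 14 d. The lag is 0, or 2-4 h if section 1.4 means that levels only start to rise then.

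Example (T 5 d, tmax 8 h, no lag): ke = 0.00578/h, ka = 0.582/h.
- C4/C8 = (0.977 - 0.097)/(0.955 - 0.009) = 0.93.
- AUC from 0 to t is proportional to (1 - exp(-ke t))/ke - (1 - exp(-ka t))/ka, which gives 6.12 to 8 h and 20.7 to 24 h, a ratio of 0.30.

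| Quantity | No lag | Lag 2-4 h |
|---|---|---|
| C4/C8 | 82%-96% | 0%-88% |
| AUC0-8 / AUC0-12 | 58%-63% | 39%-56% |
| AUC0-8 / AUC0-24 | 26%-30% | 14%-24% |

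Levels are still rising from 4 h to 8 h in every case, and AUC0-8 covers neither a 12 h nor a 24 h dosing interval.

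**5. The later draws.** C2D1 and C3D1 each give one pre-dose level during continuous dosing. A single point gives no slope, and 21 days of doses separate the two draws.

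**The case against.** The strongest reply is that half-life information is present even without a slope, through accumulation. It is. On the model above, with once-daily constant dosing, the C2D1 trough divided by the C1D1 8 h level is the sum of C(24j) for j = 1 to 21, divided by C(8). This is about 6.7-7.4 at 5 d and 13.0-13.7 at 14 d, with a lag of 0 to 4 h. That roughly two-fold gap could be detected. So a reader who infers that quinacrine half-life cannot be estimated at all goes too far. What stands is that no slope-based estimate is possible on the section 1.4 figures, that no accumulation model is planned, and that any such estimate would depend on its assumptions and on the dosing history.

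A reader might also infer that the trial will report an invalid half-life. The documents do not establish that. The conclusion depends on section 1.4 being right, the source of the 4 h is not shown, and an analyst could report T1/2 as not estimable.

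A third tempting step is to say that dose changes ruin a C3D1-to-C2D1 trough comparison. Section 11.5 plans no such comparison. Section 3.1 does say "Intra-patient dose escalation will occur only for patients experiencing Common Toxicity Criteria" below grade 2 on a previous course, but its next sentence holds escalation for lower-cohort patients until the highest-dose cohort patient has completed a first cycle. A doubling at cycle 2 therefore cannot be taken as the typical case. Holds and reductions are possible (section 5.1: "quinacrine will also be delayed/ dose-reduced"), which is reason enough to describe troughs by dose received, but no more.

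Finally, AUC0-8 can be computed from the existing draws. The defect is the missing label.

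**Conclusion.** The point holds as an internal contradiction with a limited consequence. Sections 1.4 and 8.1.1 differ 30- to 84-fold on quinacrine half-life. If section 1.4 is right on half-life and time of peak, the planned draws contain no post-peak series and T1/2 cannot be obtained from a slope. The AUC interval is undefined whichever half-life is right.

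The contradiction, the missing post-peak draws and the missing interval are read directly from the documents. The percentages in step 4 rest on an assumed one-compartment model and on how the 2-4 h rise is read. Only their direction should be relied on.

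Severity is minor. PK is exploratory (sections 2.5 and 8.1.1) and is analysed in a batch at study end (Appendix A), so the MTD, RP2D, primary endpoints and sample size are untouched. It would be wrong to infer any effect on dose finding. The half-life conflict does not reach capecitabine, although 8.1.1 leaves its AUC interval unstated too.

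**What to change.** First reconcile sections 1.4 and 8.1.1 on quinacrine half-life and time of peak, and cite the source of the figure that is kept.

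If the section 1.4 figures stand, amend 8.1.1 and 11.5 as follows:
- Delete quinacrine T1/2, or label it as a model-based estimate from trough accumulation that uses each patient's actual dosing history, with its assumptions stated.
- Define quinacrine AUC as observed AUC0-8 on C1D1, without extrapolation.
- Report quinacrine Cmax as the maximum observed up to 8 h.
- Summarise the C2D1 and C3D1 troughs descriptively by dose actually received.

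State the capecitabine AUC interval in 8.1.1 in the same amendment. Keep all existing draws.

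The cost is a text change, with no extra blood, visits or assays. Because PK is batched at study end, it can be made before any PK analysis. The price is that no slope-based quinacrine half-life and no total exposure are reported. If the sponsor wants a slope-based half-life, it needs several draws over days after the last dose, which the plan does not have. For an exploratory aim, deletion or relabelling is the simpler choice.
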